**A Comparative Randomized Controlled Pragmatic Trial of
Neurofeedback and Working Memory Training for Children with
Attention-Deficit/Hyperactivity Disorder: Protocol**

Abstract

Today, the treatment for children and adolescents with Attention Deficit/Hyperactivity Disorder (ADHD) is predominantly pharmacological. However, not all individuals respond to medication or experience side effects. In addition, the compliance and treatment fidelity to medication is sometimes limited, why effective non-pharmacological treatment options are desirable. Neurocognitive training (NCT) methods such neurofeedback (NF) and working memory (WMt) have shown efficacy to treat the primary symptoms of ADHD in non-blinded trials. Still, larger, comparative and blinded pragmatic randomized trials are needed to ensure their efficacy and effectiveness, and to identify an optimal training rationale. Furthermore, little is known about predictors of treatment response to NCTs, such as genetic variants. In this article we present the protocol of a randomized controlled pragmatic trial. Three NCT methods, namely two NF variants, Slow Cortical Potential training (SCP), and Live Z-Score training (LZS), as well as Working Memory Training (WMt) are evaluated against each other and a waiting list control/treatment as usual only group. In a clinical outpatient setting, N = 200 children and adolescents with ADHD aged 9-17 years and common comorbidities are randomized to one of the treatment groups or the inactive control group (n=50/group). The treatment groups (SCP/LZS/WMt) receive a total of 25 highly frequent training sessions (5/week for 5 weeks). A comprehensive assessment comprising ADHD core symptoms, psychopathology, neuropsychology, neurophysiology, quality of life and health related measures are collected pre and post treatment as well as at a 6-month follow-up. Primary outcomes are blinded teacher and unblinded parent ratings as well as self-ratings on the Conners 3 for ADHD. We expect that participants receiving NCT will exhibit improved core ADHD symptomatology compared to waiting list controls. Moreover, we hypothesize that type of NCT (SCP, LZS, WMt) and participant characteristics, such as genetic predisposition, age, IQ, gender, verbal skills, and comorbidity predict patterns of treatment effects the various outcomes.

Key words: ADHD, ADD, comorbidity, attention, treatment, neurofeedback, working memory training, RCT, evidence-based, intervention

Study protocol

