After referral or self-referral and initial evaluation based on requisitioned report on previously made assessment to establish AD/HD diagnoses the study participants are randomized to four different groups N=50 in each. Two groups of NF (SCP and Ft), WMt group, and the fourth, control group will be measured during treatment as usual (TAU) and will be able to train with self-preferred method after the last measure point. The duration of KITE study is 36 months. After initial screening the duration for participants in the study is approximately 30 weeks a total of; (a) baseline testing, (b) 5 weeks of CLT/TAU, (c) post testing and (d) six months follow-up testing. All the participants attend the study in parallel with TAU, such as drug treatment.

Inclusion criteria

Clinical diagnosis of AD/HD according to DSM-IV-TR and the K-SADS interview, drug naive or under stable medication with stimulants or equivalent for at least 1 month.

Exclusion criteria

IQ <80 (WISC-IV or WAIS-IV), clinically unstable psychiatric condition such as suffering from acute depression, bipolar disorder, severe obsessive compulsive disorder, clinically judged severe self-harming behavior, severe somatic (neurological) disease, or has a very limited knowledge of the Swedish language.

Interventions

Subjects randomized to the training groups, i.e. NF1, NF2 and WMt, comes to the clinic five times per week for five weeks, 25 sessions in total. Each session lasts about 50 minutes.

Two NF methods

NF 1: Slow cortical potential (SCP)

SCP is slower bioelectrical activity in the brain, it is a form of event related potentials (ERPs) and locked in time. It is related to phasic regulation of cortical excitability and apical dendrites of pyramidal cells are believed to be the source of the activity. SCP is characterized of negative and positive shifts lasting from 350(?) milliseconds to several seconds. The negative shift is believed to reflect brain state of allocating attentional resources and increased cortical excitability, and positive shifts reflects inhibition, reduced excitability. In this

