Flankers test which is a kind of reaction time task and where the subject has to respond as quickly as possible, while avoiding errors. The participants are required to indicate the direction of a central target in an array of three stimuli. *Continuous performance test, CPT-OX* consists of 400 letters presented briefly (150ms) every 1,65 s in a pseudorandom sequence at the centre of a computer monitor. Letter "O" is the cue and initiate 40 cue-target i.e. 'O' followed by letter 'X' (go condition) or 40 cued non-target (O followed by different letter than X, no-go condition).

Randomization

Random list of numbers. The date when consent form has arrived.

Statistical analysis

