We expect that participants receiving NCT will exhibit improved core ADHD symptomatology and secondary and exploratory outcomes compared with waiting list controls. Moreover, we hypothesize differing effects of Cognitive training in ADHD type of NCT (SCP, Lzs, WMt) based on the participant characteristics (e.g. genetic predisposition, age, IQ, gender, verbal skills, and comorbidity) will predict patterns of treatment effects on the various outcomes. The sample size calculation refers to the three primary outcome endpoints: change in Conners 3 total scores and subscales for parent, self-report, and blind teacher ratings between baseline and follow-up assessment, in the Intention to Treat (ITT) sample. MANOVA for repeated measures (three measurement points, withinbetween subjects' interactions, posthoc tests) will be used for the statistical analysis for the RCT study. Based on available evidence about NCT efficacy medium effects for the primary outcomes are expected. With N=200 (n=50 SCP vs. n=50 Lzs vs. n=50 WMtr vs. n=50 TAU only controls) and alpha=5%, the power (1-beta) is >99% for medium effects (G Power 3.1.7). All data provided for the participants will be included in the analyses. Data will be tested for normality and homogeneity of variance. To verify that the treatment group and control groups are comparable for continuous and categorical demographic variables at pretreatment, a series of independent-samples t-tests and chi-square tests will be conducted. As for primary outcomes, analyses for secondary outcomes will be conducted according to ITT principles. To analyse for the significance of potential factors predicting outcomes (age, IQ, language abilities, gender, comorbidity, genetic variants) in the active NCTs training groups, these are analysed using a logistic regression to explain dichotomized (by median-split) Conners 3 outcomes as the dependent variable.

Adverse events

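### Medication status at entry is neither a stratum nor a covariate, so its balance across four arms of 50 is left to chance; the randomization section also does not assure 50 per arm

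*Combined protocol and SAP*

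**What the plan says.** The Randomization section consists of two fragments: "Random list of numbers. The date when consent form has arrived". The documents say nothing more about how the list was built or used.

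Three places give equal arms. The abstract says children "are randomized to one of the treatment groups or the inactive control group (n=50/group"). Eligibility and Recruitment says "the study participants are randomized to four different groups N=50 in each". The Statistical analysis section bases its power statement on "n=50 SCP vs. n=50 Lzs vs. n=50 WMtr vs. n=50 TAU only controls".

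On medication, the inclusion criteria admit children who are "drug naive or under stable medication with stimulants or equivalent for at least 1 month". Drug treatment may continue in every arm as part of treatment as usual (TAU). The primary analysis is "MANOVA for repeated measures (three measurement points", with group-by-time interactions and post hoc tests), and no covariate is named. Comparability at baseline is to be checked with t-tests and chi-square tests on demographic variables. The planned predictor analysis lists age, IQ, language, gender, comorbidity and genetic variants. Medication is not on that list.

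**The concern.** Two things looked wrong.

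First, an unrestricted list of random numbers almost never yields four arms of exactly 50, and the text does not show that the list is restricted.

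Second, medication status is known before allocation, could plausibly relate to change on the Conners 3, and differs between children by design of the eligibility criteria. If neither allocation nor analysis takes account of it, a between-arm difference in outcome can be challenged as a difference in medication mix. That matters most for key objective (i), the comparison of training methods, which rests on pairs of about 50 children. It matters less for pooled neurocognitive training (NCT) against TAU. The baseline tests would at best reveal an imbalance; they do not correct one.

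**Working it through.** **Inputs.** From the documents: N = 200, four arms of 50, three measurement points, alpha 5%. Assumed, because the documents give no figure: medium effect f = 0.25 (d = 0.5 for a pair), 50-80% of children medicated at entry, and a 0.5 SD difference in change between medicated and drug-naive children.

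**1. The plan's own power figure.** The plan states that "the power (1-beta) is >99% for medium effects (G Power 3.1.7"). For the within-between interaction, the noncentrality is λ = f²·N·m/(1−ρ), with 6 and 392 degrees of freedom under sphericity. With ρ = 0, λ = 0.0625 × 200 × 3 = 37.5 and power is 0.9989; for ρ from 0.3 to 0.7 it is above 0.9999. The Pillai variant, with λ = N·s·f² = 200 × 2 × 0.0625 = 25, gives 0.978. The stated figure is therefore reproducible. For a single pair at d = 0.5, 50 v 50, power is 0.697 (noncentral t).

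**2. Arm sizes, if the list were unrestricted.**
- P(50, 50, 50, 50) = 200!/(50!⁴ × 4²⁰⁰) = 0.00036.
- SD of one arm = √(200 × 0.25 × 0.75) = 6.1, with a 95% range of 38-62.
- The mean smallest arm is 42.8, and P(smallest arm ≤ 40) = 0.23.
- Mean pairwise power at d = 0.5 is 0.691 against 0.697 at 50 v 50; at 40 v 60 it is 0.679.

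Unequal arms therefore cost about 0.6 points of pairwise power on average.

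**3. Medication mix with exactly 50 per arm.** The medicated children are distributed over the arms by a multivariate hypergeometric draw (400,000 draws per row). One child is 2 percentage points, so 15 points or more means at least 8 children.

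| Medicated (assumed) | Median largest gap | P(largest gap ≥ 10) | P(largest gap ≥ 15) | P(pooled NCT v TAU ≥ 10) |
|---|---|---|---|---|
| 50% | 14 points | 0.80 | 0.44 | 0.25 |
| 60% | 14 points | 0.79 | 0.42 | 0.24 |
| 70% | 12 points | 0.76 | 0.36 | 0.21 |
| 80% | 12 points | 0.67 | 0.24 | 0.15 |

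The largest gap is taken over all six pairs of arms. For one pair named in advance, P(gap ≥ 15 points) is 0.06-0.13.

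**4. Effect on a contrast.** Shift = difference in medicated share × difference in change = 0.15 × 0.5 SD = 0.075 SD. The standard error of a pairwise difference is √(2/50) = 0.20 SD, so the shift is 0.075/0.20 = 0.375 standard errors. The share of outcome variance explained by status is p(1−p) × 0.5²: 0.25 × 0.25 = 6.25% at p = 0.5, and 0.16 × 0.25 = 4% at p = 0.8.

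**5. After the change.** If all 200 children were allocated in blocks stratified by medication, arms would be 49-51 with a largest gap of at most 2 points (block size 4), or 48-52 with at most 4 points (block size 8). A list fixed at 50 per arm but without strata leaves the gaps in step 3 as they are.

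**The case against.** A reader might infer that the list is unrestricted and that the trial will therefore miss 50 per arm. The text does not say so. A shuffled list of 200 entries, 50 per arm, fits the same words and agrees with the stated arm sizes. Use in order of consent arrival is itself an inference from the second fragment. All that can be said is that 50 per arm is not assured. Nor does the arm-size question undermine the power statement, as steps 1 and 2 show.

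It is also fair to say that the medication effect is modest and rests on two assumed values. Chance imbalance under randomization is already reflected in the standard error, so it is imprecision and not bias. An imbalance is likely in some pair only at about 10 points; at 15 points the odds are below even, and lower still for a pair named in advance. The endpoint is change, medication must be stable at entry, and methylphenidate is washed out for 48 hours before measurement. These features may narrow the prognostic difference, but nothing in the documents shows that they remove it.

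Finally, enrolment began in August 2013 (Trial status), so a new list may reach only part of the sample. If 100 children had already been allocated by an unrestricted list (assumed), final medicated counts would still differ by more than 2 between arms in about 96-98% of trials. For this reason covariate adjustment has to come first and stratification second.

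None of this answers the central point. With 50 per arm fixed, medication mix is still left to chance and the planned model does not adjust for it.

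**Conclusion.** The point holds in limited form. The randomization section omits list type, blocking and stratification, so 50 per arm is not assured; the consequence for power is negligible and the stated figure above 99% stands. Medication status at entry is neither a stratum nor a covariate, and this does not depend on what kind of list was used. With 50-80% medicated (assumed), some pair of arms will probably differ by 10 points or more, and a 15-point gap has a probability of 24-44%. Under an assumed 0.5 SD difference in change, 15 points is worth 0.075 SD. That is small beside a medium effect of 0.5 SD, but it is enough to leave a small between-method difference open to dispute when pairwise power is only about 0.70. A reader might take this as evidence of systematic bias in the randomization; the documents do not support that. The loss is in precision and interpretability.

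**What to change.** 1. Prespecify medication status at entry (drug naive v stable medication) as a factor in the primary analysis for all participants. It should enter together with its interaction with time, so that the group-by-time test is adjusted. This works even if allocation is complete.
2. State in the Randomization section what kind of list is used and how arm sizes are controlled. If a list fixed at 50 per arm already exists, saying so settles the arm-size question.
3. For children still to be allocated, use 1:1:1:1 permuted blocks of varying size (4 and 8), stratified by medication status.

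The cost is one or a few degrees of freedom, a new list, a paragraph of text and slightly more administration, with no extra participants or visits. Blocks bring some predictability near their ends, which varying the size limits. Near-exact balance is reached only if most children are allocated under the new scheme; otherwise the gain comes mainly from the first step.

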Guidelines recommend multimodal treatment combining psychosocial and educational interventions with medication. Compared with psychopharmacological treatment studies there are quite a limited number of studies on alternative treatments for children and adolescents with AD/HD²⁰. CLT's are non-invasive methods and above all NF has shown good preliminary evidence in several international studies in reducing the core symptoms of AD/HD in children, and has encouraging results in contrast to psychopharmacological treatment that the positive effect persists²¹. WMt has promising evidence of improving working memory capacity and that the good effects also can generalize into other functions but there are a clear shortage of studies comparing WMt with other active interventions and controls (Melby-Lervåg, 2012). If the results would be positive then CLT's could broaden the range of treatment for children and adolescents with AD/HD in Sweden. To date there are several different kinds of neurofeedback training options and two mainstream methods are Slow Cortical Potential training (SCPt) and frequency training (Ft) whereas the latter offers more commercially available options. For the clinical validity of this rather extensive training it is of major importance that potential improvements also last. There is a lack of follow-up studies concerning CLTs (Hodgson et al, 2012, Lofthouse et al, 2012, Melby-Lervåg et al, 2012) and the aim of this sub study is to measure long term outcome from CLT methods

Aims and objectives

Primary aim of the study is to evaluate if neurocognitive training improves core symptoms in AD/HD. Key objectives are (i) are there differences in outcome between the different neurocognitive methods, (ii) can we find predictors that differentiate learners from non-learners, (iii) are neurocognitive methods feasible in clinical settings. Additional important research questions are a) if possible improvements generalize to other settings like

school and home environment, b) does effects last six months after training, c) does the training affect the bioelectrical communication in the brain, d) are there more generalized beneficial outcomes as in perceived quality of life, stress in parents, sleep patterns.

Method/design

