KITE study use a computerized software program for working memory training called Memory Quest Flex (www.flexprogram.org). Every session consists of ten different modules with eight (for younger children) or 10 (from 12 years old) different exercises in each. The different exercises stresses on either visual or auditory working memory, and the difficulty level adjusts automatically as a response to individual performance. Various kinds of positive rewards, e.g. oral and collect objects, is provided by the program. After follow-up measure participants in the WMt group are offered NF2 training in the same way as NF2 group are training.

Control

For those randomized to control group are measures collected at the same time points as for the active groups. After final data collection participants in the control group are offered NF training same as the active NF groups have obtained.

Measures

Participants using methylphenidate has a 48 hours wash-out period before measurement.

Primary outcome measures

The primary outcomes for KITE study is changes in AD/HD core symptoms measured by self-, parents- and teacher estimates by full-length Conners 3²³ forms. Conners 3 is a well-studied rating scale aimed to capture manifestations of the behavioural symptoms in AD/HD. It consists of three questionnaires (child, parent and teacher) for children between 6-17 years old.

Secondary outcome measures

Rating scales

*Behavior Rating Inventory of Executive Function (BRIEF)*²⁴ is used for parents and teachers to fill to identify dysexecutive functioning and possible improvements with neurocognitive training. It is an [86-item questionnaire](#).

KIDSCREEN-27^{25,26}; is a self-report questionnaire consisting of 27 items applicable to children between 8-18 years about perceived quality of life (QoL). Items are scored on a five-point scale; higher scores indicate better experienced QoL. The KIDSCREEN-27 has been shown to have robust psychometric properties²⁷.

*The Swedish Parenthood Stress Questionnaire (SPSQ)*²⁸ is developed from Parenting Stress Index (PSI)²⁹ and consists of 35 questions divided into five domains. The aim is to detect perceived stress related to parenthood.

*Diet and exercise questionnaire*³⁰; Swedish National Food Administration's published diet and exercise questionnaire for adults has been slightly adjusted to suit children, and parents fills it at the first measure point.

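### Three primary Conners 3 raters, with totals and subscales in four arms, share one 5% alpha with no adjustment, lead score or success rule, so the error rate of the primary claim is undefined

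*Combined protocol and SAP*

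**What the plan says.** The Statistical analysis section ties the sample size to "three primary outcome endpoints: change in Conners 3 total scores and subscales for parent, self-report, and blind teacher ratings", taken as change from baseline to follow-up. Each rater therefore contributes totals and subscales, and the number of subscales is not given.

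The analysis is given as "MANOVA for repeated measures (three measurement points, withinbetween" interactions, and the sentence ends "posthoc tests) will be used for the statistical analysis for the RCT study". Alpha appears once, in the power sentence: "and alpha=5%, the power (1-beta) is >99% for medium effects".

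Two other places name the same raters without ranking them. The Abstract says "Primary outcomes are blinded teacher and unblinded parent ratings as well as self-ratings on the Conners 3 for ADHD". Primary outcome measures says "changes in AD/HD core symptoms measured by self-, parents- and teacher estimates".

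Aims and objectives lists as key objective (i) "are there differences in outcome between the different neurocognitive methods", which adds comparisons among the three active arms.

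No section gives an adjustment, an alpha split, a hierarchy, a lead score, a correction for the post-hoc tests, or a rule on whether one or all raters must be positive. None says whether the MANOVA is joint over raters or run separately for each.

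**The concern.** With several primary results and one alpha, the plan has to say which pattern of results counts as success. Here a mixed pattern is easy to foresee, because the teacher is blinded and the parent is not. If the parent total is significant and the teacher total is not, the text does not say whether the primary aim has been met.

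Two things are at stake. First, control of the familywise error at 5% cannot be verified. Second, the deciding score (total or a subscale) and the success rule could be settled after the results are known. A reader could adjust over three raters afterwards, but only if one score per rater had been fixed beforehand.

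**Working it through.** **Inputs from the Statistical analysis section:** 4 arms of 50 (N=200), three raters, three measurement points, alpha 5%, medium effects (no number given).

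**Assumed, because the documents give no figure:** rater correlation 0 to 0.9; correlation over time 0.5 unless stated; medium taken as f=0.25 or as d=0.5.

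**1. The plan's own figure.** For the group-by-time test with f=0.25:
- Repeated-measures formula: λ = f²·N·m/(1−ρ) = 0.0625×200×3/(1−ρ), which is 37.5 at ρ=0 and 75 at ρ=0.5, with df 6 and 392. Power is 99.9% and above 99.99%, so the stated figure reproduces.
- A MANOVA variant: λ = f²·s·N = 0.0625×2×200 = 25, with the same df, gives 97.8%, slightly below it.

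This power is for an omnibus test at an undivided 5%.

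**2. Error rate under each reading.** For three independent tests at 5%, 1−0.95³ = 14.3%; the ceiling is 3×5% = 15%. With correlated raters I used simulation: one total per rater, a Wilks test of the two change scores over four arms, no true effect, 20,000 runs per setting, simulation error at most about 0.25 points.

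| Rater correlation | Any of 3 group-by-time tests | Any of 3 pooled NCT-vs-TAU contrasts | Joint MANOVA gate | Gate, then any rater's own test | Holm over 3 raters |
|---|---|---|---|---|---|
| 0 | 14.4% | 14.4% | 5.1% | 4.4% | 4.9% |
| 0.3 | 13.9% | 13.6% | 5.1% | 4.2% | 4.8% |
| 0.5 | 13.3% | 13.0% | 5.4% | 4.0% | 4.7% |
| 0.7 | 11.1% | 10.9% | 4.9% | 3.2% | 3.9% |
| 0.8 | 10.6% | 10.1% | 5.0% | 2.9% | 3.7% |
| 0.9 | 9.1% | 8.4% | 5.1% | 2.7% | 3.1% |

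A large-sample check (chi-square, 6 df) gives 14.2%, 12.9%, 11.4% and 8.7% for the first column at 0, 0.5, 0.7 and 0.9. If all three raters must be significant, the rate is 0.0-2.1%.

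**3. Benefit only.** The hypothesis is directional. Counting only false superiority of pooled training over TAU on any rater, simulation gives 6.8%, 6.1%, 5.2% and 4.4% at rater correlation 0, 0.5, 0.7 and 0.9. The comparator is 2.5%, not 5%.

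**4. The joint gate when one rater has a real effect.** With d=0.5 on one rater only, a false claim on another rater gets through the gate in 7.7-9.1% of runs (group-by-time) or 6.9-8.4% (pooled contrast). Holm over raters gives 3.8-4.3% (group-by-time).

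**5. Further comparisons.** If any active arm versus control on any rater sufficed (3×3 = 9 unadjusted tests), the rate would be about 33%, 26% and 20% at correlation 0, 0.7 and 0.9. Subscales cannot be costed, because their number is not given.

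**6. Limits on the remedy.**
- All pairwise tests number 6 pairs × 3 raters = 18. Holm over three raters beside a separate Holm over these 18 gives about 6-7.5% in total at correlation 0-0.7, so the two families cannot each have 5%.
- A significant four-arm test does not show benefit. With one method 0.35 SD better, another 0.35 SD worse, and pooled training equal to TAU, the per-rater test is significant in about 86-87% of runs.

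**The case against.** The strongest objection is that 11-14% belongs to a rule the plan never states. That stands. A reader might infer that the trial runs at that error rate, or that the plan lets any single rater carry the claim; the documents support neither. A requirement on all three raters, or a joint test as a gate, is equally compatible with the text. The question "if possible improvements generalize to other settings like" school and home is no evidence for an any-rater rule either, since it is listed among additional research questions, apart from the primary aim and the key objectives.

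Direction matters too: the larger figures count significance either way, and omnibus results that come only from differences among methods. Counting benefit alone roughly halves them, but it halves the nominal level as well, so inflation remains.

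A reader might also infer that a rater could be quietly dropped. Three sections name all three raters as primary, so that would be visible. What remains open is the score and the success rule.

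Finally, MANOVA might be thought to deal with multiplicity. The text applies it to the measurement points and never says that raters are pooled. Even if they were, the gate would not control claims on single raters once one rater has a real effect.

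**Conclusion.** The omission is certain: there is no adjustment, lead score or success rule for three raters with totals and subscales in four arms. Control at 5% therefore cannot be verified; whether it fails depends on the reading.

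- Any one total suffices, each tested at 5%: about 11-14% at rater correlation 0-0.7 and 8-9% at 0.9. For false benefit alone, about 5-7% and about 4%, against 2.5%.
- All three raters required: no inflation.
- Joint gate: about 5% when nothing works, but about 7-9% false claims on another rater when one rater has a real effect of d=0.5.

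These rates rest on assumed correlations and on one total per rater; subscales or unadjusted post-hoc tests would raise the first. Confidence is high in the omission and conditional for the rates. This should be fixed.

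**What to change.** Amend the Statistical analysis section before any unblinded analysis:

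1. Name one Conners 3 score per rater as primary and make the subscales secondary.
2. Test the three raters with Holm at a familywise 5%. Word a pass on the four-arm group-by-time test only as showing that the arms differ for that rater, since it does not by itself show training better than TAU.
3. Label pairwise arm comparisons, including those between methods under key objective (i), as not confirmatory. Alternatively, test them only for raters that pass step 2, with a stated adjustment that keeps the overall familywise error at 5%. A separate Holm over 18 tests alongside step 2 does not do that.

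**Cost.** No new data are needed, but the trial is registered (Method/design) and has enrolled since August 2013 (Trial status), so this is a formal amendment. Subscale results would no longer be confirmatory.

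Power falls at the strictest Holm step, 0.05/3 = 0.0167. With an assumed d=0.5 for each training arm versus TAU, group-by-time power per rater goes from about 50% to 32% at time correlation 0.2, 74% to 57% at 0.5, and 99% to 98% at 0.8. Under f=0.25, the value that reproduces the stated figure, it stays at about 99.6% or more by the repeated-measures formula, or about 94% by the MANOVA variant. The amendment should therefore also state what medium means and which time correlation is assumed.
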